### 3.2 Part B

Part B is a multiple ascending dose study design. Subjects will receive either PK10571 or placebo. Approximately 24 subjects will be enrolled in Part B. Subjects will be enrolled in 3 cohorts of 8 subjects each.

Gossamer Bio, Inc.

The initial dose for Part B will be determined after review of the safety and pharmacokinetic data from Part A by the Safety Review Committee.

Data from the lower dose cohort will be analyzed before deciding whether to proceed with the higher dose cohort. Alternatively, a lower dose may be administered, depending upon review of previous cohort's safety and pharmacokinetic data.

Subjects will receive one of the treatments listed in Table 3. The assigned treatment will be given either as a single daily dose (QD), or divided into two daily doses (BID), or divided into three daily doses (TID; each dose to be separated by 6 hours on a given day).

Subjects will be assigned to either active treatment or placebo in randomized fashion.

Table 3Part B: Planned Doses for Cohorts 1–3

| Cohort                 | Test Formulation (n = 6) | Placebo (n = 2) |
|------------------------|--------------------------|-----------------|
| 1                      | PK10571 initial dose     | Placebo         |
| 2                      | PK10571 mid dose*        | Placebo         |
| 3                      | PK10571 high dose*       | Placebo         |
| n = number of subjects |                          |                 |

n = number of subjects

Note: The dosing regimen will be either once daily (QD), twice daily (BID), or three times daily (TID) for 7 consecutive days. For TID dosing, each daily administration will be separated by 6 hours.

\* Alternately, Cohort 2 or 3 will receive a lower dose, depending upon safety and pharmacokinetic data from Cohort 1 or 2, respectively.

Each dose will be administered using an oral inhalation device. Meals will be the same and scheduled at approximately the same times relative to dose for each cohort, if possible. Refer to Section 5.5.1 for details regarding timing of meals for each proposed dosing regimen (QD, BID, and TID).

No water may be consumed for 1 hour prior through 1 hour after each dose, except for 60 mL of room temperature water which will be given to subjects to rinse their mouths after dosing. Subjects will swish the 60 mL of water in their mouths then spit it out.

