## APPENDIX 4 PART B: MAD TWICE DAILY (BID) DOSING

The Safety Review Committee will review the safety data (including local irritation) and pharmacokinetic data from the SAD protocol (Part A) to determine the starting dose for the first MAD cohort and if the first cohort of the MAD protocol should be dosed QD (once daily), BID (twice daily; once every 12 hours), or TID (three times daily; 6 hours between each dose for a given day of dosing).

If the decision is made to start dosing in the MAD protocol at BID, then the Safety Review Committee will review the safety data (including local irritation) and PK data from the first MAD cohort to determine if BID dosing should continue, if dosing should be reduced to QD, or if dosing should be increased to TID for the next cohort.

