6.2.10. Concentration-Time Data

PART A:

Blood samples for pharmacokinetic analysis of PK10571 will be collected at 0 hour (predose), and then at 3, 10, 20, 30, 40 minutes, and 1, 2, 4, 8, 12, 24, 36, and 48 hours after study treatment administration as specified by the protocol amendment. For two blood samples were collected at 1 and 5 minutes, instead of one blood sample at 3 minutes, prior to the protocol amendment. For and above, the 3-minute sample was collected after the protocol amendment.

PART B:

If QD dosing: Blood samples for pharmacokinetic evaluation will be obtained prior to the first dose administration (predose) on Day 1 and Day 7, and at the following times: Day 1 and Day 7 at 3, 10, 20, 30, and 40 minutes and 1, 2, 4, 8, 12, 24, and 36 hours after dosing; predose on Days 3-6, and on Day 8, Day 9, Day 10, Day 14, and Day 35 (total 34 samples).

If BID dosing: Blood samples for pharmacokinetic evaluation will be obtained prior to the first dose administration (predose) on Day 1 and Day 7, and at the following times after each dose (2 per day) on Day 1 and Day 7: 3 and 30 minutes and 2, 8, and 12 hours. Blood samples will also be collected before the first dose on Days 3-6, and on Day 8, Day 9, Day 10, Day 14, and Day 35 (total of 30 samples).

If TID dosing: Blood samples for pharmacokinetic evaluation will be obtained prior to the first dose administration (predose) on Day 1 and Day 7, and at the following times after each dose (3 per day) on Day 1 and Day 7: 3 and 40 minutes and 6 hours. An additional sample will be obtained on Day 2 (12 hours after the 3rd dose on Day 1). Blood samples will also be collected before the first dose on Days 2-6, and on Day 8 (6 hours and 12 hours after the 3rd dose on Day 7), Day 9, Day 10, Day 14, and Day 35 (total of 30 samples).

For multi-capsule administrations (if required to achieve the dose), the first postdose blood collection will be performed 5 minutes after the start of study treatment administration.

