V _z /F	Apparent volume of distribution in the terminal phase (Day 7 only), presented to 3 significant figures	
	Vz/F will be presented with and without weight-adjustment. Weight adjustment will be calculated as Vz/F x 70/body weight in kg.	
Rac	Accumulation ratio during multiple dosing; presented to 3 significant figures and calculated as:	
	RAC=AUC ₀₋₂₄ Day 7/AUC ₀₋₂₄ Day 1	
$\lambda_z \left(K_{el} , \right. \\ Lambda z)$	Apparent terminal elimination rate constant calculated by linear regression of the terminal linear portion of the log concentration versus time curve (Day 7 only), presented to 3 significant figures	
Т½	The observed terminal elimination half-life, presented to 3 significant figures and calculated as:	
	$T_{1/2} = \ln(2)/\lambda_z$ (Day 7 only)	

No value for λ_z and other λ_z -related parameters (AUC_{inf}, $T_{1/2}$, etc.) will be reported if λ_z cannot be estimated.

PK concentration data will be summarized by study part, treatment, and day (for MAD study part) at each nominal sample time. PK parameter data will be summarized by study part, treatment, and day (for MAD study part). PK parameter data will also be stratified by sex and for males and females combined. PK parameter tables will include columns for baseline BMI, FEV1, and FVC.

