6.3. Conventions

All clinical summaries, figures and statistical analyses will be generated using SAS (Version 9.4 or higher)².

Summaries of the clinical data will be presented by treatment group. In addition, disposition, demographic, and baseline summaries will include an overall column that consists of all subjects.

PK data listings, summaries, figures, and statistical analyses will be generated using Phoenix[™] WinNonlin[®] (Version 6.3 or higher) or SAS (Version 9.4 or higher).

Treatment group labels will be displayed as follows:

Cohort	Test Formulation
1	Placebo
1	PK10571 FPD
2.	Placebo
2	PK10571 FPD
3	Placebo
3	PK10571 FPD
4	Placebo
4	PK 10571 FPD
5	Placebo
5	PK10571 up to FPD

Cohort	Test Formulation
1	Placebo
1	PK10571 initial dose
2	Placebo
2	PK10571 mid dose*
2	Placebo
3	PK10571 high dose*

Note: The dosing regimen will be either once daily (QD), twice daily (BID), or three times daily (TID) for 7 consecutive days. For TID dosing, each daily administration will be separated by 6 hours. Placebos will be grouped together within summary tables.

*Alternately, Cohort 2 and 3 will receive a lower dose, depending upon safety and pharmacokinetic data from Cohort 1 or 2, respectively.

The initial (lower) dose for Part B will be determined after review of the safety and pharmacokinetic data from Part A.

The data from the lower dose cohort will be analyzed before deciding whether to proceed with the higher dose cohorts.

Listings will be sorted in the following order: treatment, subject, parameter, and visit unless otherwise stated. All data will be listed.

For clinical data, continuous variables will be summarized by the number of non-missing observations, mean, median, standard deviation, and minimum and maximum.

PK data (concentration-time data and PK parameters) will be summarized by (n), mean, standard deviation (SD), median, minimum (min), maximum (max), and coefficient of variation (CV%). In addition, the geometric mean and geometric CV% will be reported for all PK parameters except T_{max}. T_{max} will be presented as median, minimum, and maximum.

Baseline values for FEV1, FVC, and BMI, defined as the values obtained prior to and closest in time to the first dose, will also be summarized by the number of non-missing observations (n), mean, standard deviation (SD), median, minimum (min), maximum (max), and coefficient of variation (CV%).

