6.11. Pharmacokinetic and Statistical Analyses

Pharmacokinetic analyses are outlined below. Other exploratory analyses may be conducted as well.

Statistical Comparison: Single Dose (Day 1, Reference) and Multiple Dosing (Day 7, Test): Part B

Comparison of the log-transformed pharmacokinetic parameters C_{max} and AUC_{0-24} for PK10571 across study days (Day 7 vs. Day 1) will be performed using an ANOVA model and the two one-sided t-tests procedure. The ANOVA model will include factors for subject, day, and cohort. The ratios of the geometric means and 95% confidence intervals will be reported. Statistical analyses will be performed using appropriate software, e.g., PhoenixTM WinNonlin® (Version 6.3 or higher, Certara L.P.) and/or SAS® (Version 9.3 or higher, SAS Institute Inc.).

SAS code will be of the form:

Assessment of Dose-proportionality: Power Model

The relationship between dose and exposure parameters will be examined graphically for Part A (C_{max}, AUC_{last}, AUC₀₋₂₄, and AUC_{inf}) and Part B (C_{max} and AUC₀₋₂₄, Days 1 and Day 7).

Evaluation of dose proportionality will be explored using power analysis.

To assess dose proportionality, the pharmacokinetic parameters after drug administration will be compared across each dose level.

Statistical analyses will be done using a power model with mixed effects (Smith, 2000)³ of the following general form:

$$ln(PK) = ln(\beta_0) + \beta_1 \cdot ln(Dose) + \varepsilon$$
,

where

PK is the pharmacokinetic parameter tested (e.g., C_{max} or AUC),

 $ln(\beta_0)$ is the y-intercept,

 β_1 is the slope (a value of $\beta_1 \approx 1$ indicates linearity), and

ε is an error term.

The estimate of slope, $\beta 1$ will be reported along with the corresponding 2-sided 95% CIs. As this is an exploratory analysis, if the 95% CI of β_1 includes 1 and/or the estimate of β_1 is relatively close to 1, PK data may appear to be dose proportional.

The SAS code will be of the form:

The Attainment of Steady-State:

The attainment of steady-state will be assessed by visual inspection of trough concentrations, and statistical assessment. For statistical assessment, linear regression of the individual trough concentrations on Days 3-7 vs time will be conducted, and the slope, 95% CI of the slope, and p-value will be estimated. If the 95% CI of the slope includes 0 and/or the estimate of slope is relatively close to 0, steady-state may appear to be reached.

Exploratory Analyses: Scatterplots

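### The Part B Day 7 versus Day 1 comparison is labelled single versus multiple dose, but under BID or TID dosing it is a day-over-day ratio that understates accumulation relative to the first dose

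*SAP*

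**What the plan says.** SAP section 6.2.11 lists a Part B parameter described as "Accumulation ratio during multiple dosing" and defined as AUC0-24 on Day 7 over AUC0-24 on Day 1. There is one formula for all cohorts. The Part B parameter list contains no AUC over a dosing interval.

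SAP section 6.11 plans an ANOVA of log Cmax and log AUC0-24, Day 7 against Day 1, under the heading "Statistical Comparison: Single Dose (Day 1, Reference) and Multiple Dosing (Day 7, Test): Part B". Neither section distinguishes between regimens.

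The regimen is left open. SAP section 6.3 notes: "The dosing regimen will be either once daily (QD), twice daily (BID), or three times daily (TID) for 7 consecutive days". Protocol Appendix 4 describes the twice-daily option as "BID (twice daily; once every 12 hours"). Protocol section 3.2 allows the daily treatment to be "divided into three daily doses (TID; each dose to be separated by 6 hours on a given day"), and Table 11 in Appendix 5 marks Day 1 doses at 0, 6 and 12 h. Sections 3 and 3.2 and Appendices 4 and 5 let the Safety Review Committee choose the regimen for the first cohort and change it for later ones.

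**The concern.** Day 1 is a single dose only if the cohort is dosed once daily. Under BID or TID the 0–24 h window on Day 1 covers two or three doses, and the Day 1 Cmax may come from the second or third of them. The reference therefore already includes build-up within the day. A reader who takes the section 6.11 heading at face value would read the ratio as exposure after repeated dosing over exposure after one dose, which it is not.

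The Safety Review Committee receives pharmacokinetic parameters by cohort and day (SAP section 7) and uses them to set the next cohort's dose and regimen. Under linear kinetics the difference always lies in the direction of less apparent accumulation, and no planned parameter or test gives accumulation relative to the first dose for a BID or TID cohort.

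**Working it through.** The documents state no accumulation ratio or half-life, so there is no figure of the plan's own to reproduce. The check compares the planned ratio with a first-interval ratio over an assumed range of half-lives.

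**Inputs from the documents.** Seven days of dosing; dose times 0 h (QD), 0 and 12 h (BID), 0, 6 and 12 h (TID); planned ratio = AUC0-24 Day 7 / AUC0-24 Day 1.

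**Assumptions.** Linear one-compartment kinetics, instantaneous absorption, equal doses, half-life 2 to 24 h. Let k = ln 2 / half-life, and scale concentrations so that one dose gives a peak of 1. Let R be the concentration left just before the first Day 7 dose.

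**QD.** With q = exp(−24k), R = q(1 − q⁶)/(1 − q). The first interval is the whole day, so both ratios equal 1 + R.

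**BID.** With x = exp(−12k) and 12 doses given before Day 7:
- R = x(1 − x¹²)/(1 − x)
- Day 1 AUC0-24, in units of 1/k: (1 − x²) + (1 − x) = (1 − x)(2 + x)
- Planned ratio: 1 + R(1 + x)/(2 + x)
- First-interval ratio, AUC0-12 on both days: 1 + R

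At 12 h, x = 0.5 and R = 0.9998. Planned: 1 + 0.9998 × 1.5/2.5 = 1.60. First interval: 2.00.

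**TID.** With y = exp(−6k):
- R = (y² + y³ + y⁴)(1 − y²⁴)/(1 − y⁴)
- Planned ratio: 1 + R(1 − y⁴)/(3 − y² − y³ − y⁴)
- First-interval ratio, AUC0-6 on both days: 1 + R

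At 12 h, y = 0.7071 and R = 1.1036 × 1.3330 = 1.471. Planned: 1 + 1.471 × 0.75/1.8964 = 1.58. First interval: 2.47.

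| Half-life | BID planned | BID first interval | TID planned | TID first interval |
|---|---|---|---|---|
| 2 h | 1.01 | 1.02 | 1.01 | 1.02 |
| 4 h | 1.08 | 1.14 | 1.07 | 1.19 |
| 12 h | 1.60 | 2.00 | 1.58 | 2.47 |
| 24 h | 2.50 | 3.38 | 2.48 | 4.55 |

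The planned ratio is 99%, 94%, 80% and 74% of the first-interval ratio for BID, and 99%, 90%, 64% and 55% for TID. With slower absorption (rate constant 2 per hour) and a 12 h half-life, the pairs are 1.63 and 2.06 (BID) and 1.61 and 2.63 (TID): the same direction and a slightly wider gap.

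**Cmax at a 12 h half-life.** The whole-day Cmax ratio is (1 + x + xR)/(1 + x) = 2.00/1.50 = 1.33 for BID and (1 + y + y² + y²R)/(1 + y + y²) = 2.94/2.21 = 1.33 for TID. Both equal the QD value. Taking Cmax from the first-dose interval on both days gives 1 + R: 2.00 and 2.47.

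**Are the samples there?** For BID, SAP section 6.2.10 schedules a predose sample and then samples at "times after each dose (2 per day) on Day 1 and Day 7: 3 and 30 minutes and 2, 8, and 12 hours", which covers 0–12 h on both days. For TID the first interval has a predose sample and only three postdose samples (3 or 5 min, 40 min, 6 h).

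**The case against.** The strongest reply is that the plan does nothing improper. AUC0-24 Day 7/Day 1 is a valid day-over-day ratio, and section 6.11's own text speaks of a comparison across study days. That stands. A reader might infer that Rac is wrong or biased as defined, but section 6.2.11 never says that it is relative to a single dose. Only the section 6.11 heading makes that claim.

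A reader might also infer that the planned ratio spoils comparison with QD cohorts. The figures do not support this. At a 12 h half-life the planned AUC ratios for QD, BID and TID are 1.33, 1.60 and 1.58, against 1.33, 2.00 and 2.47 for the first-interval version. The planned ratios lie closer together, and the planned Cmax ratio is 1.33 for all three. The results are also tabulated cohort by cohort (Tables 14.4.15 to 14.4.17).

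A third tempting step is to set the whole-day Day 7 Cmax against the Day 1 first-dose Cmax. For TID at 12 h that gives 2.94 rather than the matched 2.47, because it mixes build-up within a day with accumulation across days.

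Other points also carry weight. The gap is about 1% at a 2 h half-life. Protocol section 1.1.1 reports that accumulation did not appear to be a problem in rats or dogs, and section 1.3 describes once-daily dosing. For TID the intervals are 6, 6 and 12 h, so the repeating cycle is 24 h and AUC0-24 describes it naturally. Rac is not the only evidence on accumulation either: trough regression, Day 1 and Day 7 profiles and the Part A single-dose data are all planned. These points limit the size and priority of the concern. They do not make Day 1 a single dose under BID or TID, nor supply a planned first-dose accumulation estimate.

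**Conclusion.** The point holds as one of labelling and of a missing parameter. The single-dose description of Day 1 is correct for QD and incorrect for BID and TID; this follows from the dosing times alone. That the planned ratios understate accumulation relative to the first dose follows under linear kinetics. The amount rests on the assumed half-life and one-compartment model: negligible at 2 h, 20% (BID) to 36% (TID) below the first-interval AUC ratio at 12 h, and 26% to 45% below at 24 h. If every Part B cohort is dosed once daily, nothing changes. The documents do not support discarding the 24-hour ratio, which is a sound measure of daily exposure under a correct name.

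**What to change.** In SAP sections 6.2.11 and 6.11:

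- Use the single-dose label for QD cohorts only.
- Under BID or TID, report AUC0-24 and whole-day Cmax, Day 7/Day 1, as daily exposure ratios.
- For BID, add Rac = AUC0-12 after the first Day 7 dose / AUC0-12 after the first Day 1 dose. Take Cmax from that same first-dose interval on both days, and run the Day 7 versus Day 1 model on these quantities.
- For TID, report the matched 0–6 h AUC and Cmax ratios as supportive only, because there are three postdose samples and the dosing intervals are unequal.
- Carry the same labels into the interim outputs of section 7.

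One practical check is needed. The 12 h (BID) and 6 h (TID) samples coincide with the next dose, and Appendices 4 and 5 allow ±2 minutes without the before-dose exception that Protocol section 5.7 gives for QD. The SAP should confirm from actual times that the sample closing the interval preceded that dose.

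The cost is SAP wording and one extra partial AUC per profile, with no new blood samples. The drawback is that the TID estimate will be imprecise.

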6.3. Conventions

All clinical summaries, figures and statistical analyses will be generated using SAS (Version 9.4 or higher)².

Summaries of the clinical data will be presented by treatment group. In addition, disposition, demographic, and baseline summaries will include an overall column that consists of all subjects.

PK data listings, summaries, figures, and statistical analyses will be generated using Phoenix[™] WinNonlin[®] (Version 6.3 or higher) or SAS (Version 9.4 or higher).

Treatment group labels will be displayed as follows:

Cohort	Test Formulation
1	Placebo
1	PK10571 FPD
2.	Placebo
2	PK10571 FPD
3	Placebo
3	PK10571 FPD
4	Placebo
4	PK 10571 FPD
5	Placebo
5	PK10571 up to FPD

Cohort	Test Formulation
1	Placebo
1	PK10571 initial dose
2	Placebo
2	PK10571 mid dose*
2	Placebo
3	PK10571 high dose*

Note: The dosing regimen will be either once daily (QD), twice daily (BID), or three times daily (TID) for 7 consecutive days. For TID dosing, each daily administration will be separated by 6 hours. Placebos will be grouped together within summary tables.

*Alternately, Cohort 2 and 3 will receive a lower dose, depending upon safety and pharmacokinetic data from Cohort 1 or 2, respectively.

The initial (lower) dose for Part B will be determined after review of the safety and pharmacokinetic data from Part A.

The data from the lower dose cohort will be analyzed before deciding whether to proceed with the higher dose cohorts.

Listings will be sorted in the following order: treatment, subject, parameter, and visit unless otherwise stated. All data will be listed.

For clinical data, continuous variables will be summarized by the number of non-missing observations, mean, median, standard deviation, and minimum and maximum.

PK data (concentration-time data and PK parameters) will be summarized by (n), mean, standard deviation (SD), median, minimum (min), maximum (max), and coefficient of variation (CV%). In addition, the geometric mean and geometric CV% will be reported for all PK parameters except T_{max}. T_{max} will be presented as median, minimum, and maximum.

Baseline values for FEV1, FVC, and BMI, defined as the values obtained prior to and closest in time to the first dose, will also be summarized by the number of non-missing observations (n), mean, standard deviation (SD), median, minimum (min), maximum (max), and coefficient of variation (CV%).

Categorical variables will be summarized by presenting the frequency and percent. Percentages will be based on the number of non-missing observations or the subject population unless

otherwise specified. For each variable, all categories will be shown. Zero frequencies (but not the percent) within a category will be presented.

6.3.1. Decimal Places

Decimal places for derived data described in section 6.2.10 will be determined by the scale of measurement unless otherwise stated. No decimal places will be displayed if the smallest calculated value is ≥ 100 ; 1 decimal place will be displayed when the smallest value is within the interval (10, 100), with 10 being inclusive; 2 decimal places will be displayed when the smallest value is within (1, 10), with 1 being inclusive; and so on for even smaller scales of measurement.

Derived data where it is known in advance the result will be an integer (for example, day, month, year and number of days) will be presented with zero decimal places.

Means, medians and percentiles will be displayed to one more decimal place than the data, dispersion statistics (e.g., standard deviation) will have two more decimal places, and the minimum and maximum will be displayed to the same number of decimal places as reported in the raw data. Percentages will be displayed with one decimal place.

For PK data, individual concentrations will be reported to 3 significant figures and individual PK parameters will be reported to the precision as stated in Section 6.2.10. For summary statistics, n will be reported as a whole number; mean, standard deviation, median, minimum, maximum, and geometric mean will be reported to the same precision as for individual data. CV% and geometric CV% will be reported to 2 decimal places; p-values will be reported to 4 decimal places. Percent ratios of the geometric least squares means and associated 95% confidence intervals will be reported to 2 decimal places.

